## **Effects of Premedication with Alfentanil on Hemodynamics During and Immediately Following Electroconvulsive Therapy**

**Principal Investigator: [name]**

### **Background**

Electroconvulsive therapy (ECT) is a mainstay of treatment for patients with medication refractory mood disorders. The success of the therapy rests on achieving an adequate generalized tonic/clonic seizure. Multiple ECTS are usually required to achieve the desired effect. For the safety and well-being of the patient, a short general anesthetic is utilized during the ECT.

Electroconvulsive therapy is associated with brief, often dramatic hemodynamic alterations that are dangerous to the patient. This cardiovascular response is caused by activation of the autonomic nervous system and consists of an initial parasympathetic response rapidly followed by sympathetically mediated tachycardia and hypertension. The sympathetic response results in increased myocardial oxygen demand and ECT treatment has been associated with postprocedure increases in cardiac troponin, raising concern for clinically significant myocardial injury (Duma A, et al). The ultra-short acting synthetic opioid alfentanil has a rapid onset and duration of action that mirrors the duration of hemodynamic perturbation associated with ECT while having minimal or no effect on the duration or quality of the seizure. This drug may be effective in blunting the hemodynamic perturbations associated with ECT with minimal side effects.

Alfentanil is a FDA approved narcotic utilized to blunt the hemodynamic response to stimulating portions of a procedure at the discretion of the anesthesia provider in the conduct of general anesthesia. The effect of alfentanil on patient hemodynamics immediately following ECT has been studied only once on a small number of patients (n=21) receiving etomidate anesthesia and never on patients receiving methohexitol anesthesia (van den Broek, et al). Induction with methohexitol as opposed to etomidate is the preferred anesthetic agent as it reduces the seizure threshold in usual induction doses. We propose a double-blind, placebo-controlled study on patients receiving ECT with methohexitol anesthesia that investigates the effects of alfentanil given post-induction of general anesthesia but pre-treatment with ECT on the post-procedure hemodynamics.

### **Objectives**

To determine if the effects of alfentanil in the course of electroconvulsive therapy reduce the hemodynamic alterations during and after treatment. The hypothesis is that pre-administration of alfentanil improves hemodynamic stability in electroconvulsive therapy.

### **Methods and Measures**

A prospective, randomized, double blind, placebo-controlled AB/BA crossover study is planned in patients electively scheduled to undergo electroconvulsive therapy to treat their medication refractory mood disorders. We aim to have 200 evaluable treatments involving the consent of an estimated 100 subjects. As patients normally require more than 1 electroconvulsive therapy to treat their condition, the patient's consent will allow them to participate in this research study in each of two treatments.

Patients will undergo induction of general anesthesia with methohexitol 1 mg/kg and succinylcholine 1 mg/kg in a standardized anesthetic protocol that is nearly identical to the usual institutional standard of care for electroconvulsive therapy. A copy of the anesthetic protocol is posted for the providers reference at the point of care. Members of the study team will be responsible for randomization of the patients and preparation of the blinded study medication. Randomization to either placebo first then alfentanil or the converse will be carried out on the morning of the first study treatment and allocation concealed within a computerized randomization and data collection instrument (REDCap). Calculation of the study dose is done per the FDA package insert using an automated system within REDCap. Alfentanil (20 mcg/kg) diluted with normal saline to 10cc or placebo, consisting of 10 cc normal saline will be obtained from the OR pharmacy and placed in an identical 10 cc syringe labeled with the patient's name and "Study Drug". Any unused quantity of alfentanil will be wasted per hospital policy in the OR pharmacy. The study drug will be administered by the blinded anesthesia provider caring for the patient per the anesthetic protocol. Data will be collected by members of the study team who are blinded to the randomization. Data will be collected and secured in REDCap stored on the institution's secure internal servers.

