### **Inclusion Criteria**

Age > /=18 years

Males or females

Anticipating electroconvulsive therapy to treat refractory mood disorders

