## **Interventions and Interactions**

Informed consent will be obtained during the assessment with the psychiatrist involved in their care. The patient will be randomized into 2 groups: use of alfentanil with the first treatment or placebo with the first treatment and subsequently cross over to the other therapy for the second treatment. Study medication will be prepared by a member of the study team and the patient as well as all members performing anesthesia and data collection will be blinded to group allocation. All medications utilized in the conduct of this study are the standard anesthetic medications used on a daily basis (with the exception of the alfentanil) during the course of any patient having the ECT procedure and not enrolled in a research study.

A standardized anesthetic regimen will be utilized for each subject and includes the following:

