### **Outcome Measure(s)**

The primary outcome will be the within-individual absolute difference in systolic blood pressure from baseline to the first blood pressure after the ECT stimulus.

Secondary outcomes include the within-individual differences of heart rate at 15 and 30 seconds post stimulus, absolute difference in diastolic blood pressure from baseline to the first blood pressure after the ECT stimulus, maximum and minimum heart rates, unit doses of nitroglycerin, esmolol, phenylephrine, ephedrine, EEG and motor seizure duration, use of lidocaine, atropine or epinephrine, total in-room time, time to return of spontaneous ventilation after induction, severity of headache in the post anesthesia care unit, and satisfaction with the anesthetic post-procedure.

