### **Analytical Plan**

Results will be analyzed initially using a paired T Test for continuous variables and a Wilcoxon signed-rank test for ordinal variables.

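### Does a target counted in treatments, with no entry rule on two further treatments, leave the paired primary test short of pairs?

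*Combined protocol and SAP*

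**What the plan says.** Methods and Measures describes the design: "A prospective, randomized, double blind, placebo-controlled AB/BA crossover study is planned". It sets the size with "We aim to have 200 evaluable treatments involving the consent of an estimated 100 subjects". Two treatments are expected rather than required: "As patients normally require more than 1 electroconvulsive therapy to treat their condition", and the consent covers both. Randomisation is to an order of the two study drugs and "will be carried out on the morning of the first study treatment".

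Interventions and Interactions has each patient "subsequently cross over to the other therapy for the second treatment".

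On the number of treatments still to come, the Inclusion Criteria say only "Anticipating electroconvulsive therapy to treat refractory mood disorders". The one item in the Exclusion Criteria that counts treatments concerns those already given (at least four), not those ahead.

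The primary outcome is the "absolute difference in systolic blood pressure from baseline to the first blood pressure after the ECT stimulus". The Analytical Plan says: "Results will be analyzed initially using a paired T Test for continuous variables". The plan states no alpha, power, effect size, standard deviation, attrition allowance or replacement rule, and it does not define evaluable.

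**The concern.** The recruitment target and the primary test are counted in different units. The target is in treatments and the test is in pairs. The primary outcome can be measured at a single treatment, so on a literal reading one treatment with a baseline and a post-stimulus pressure is evaluable and adds one to the 200. A subject whose course ends after the first study treatment would then help to close enrolment but add nothing to the paired test.

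The eligibility lists do not prevent this. Every enrolled patient is already at least four treatments into ECT, so the remark that patients usually need more than one says nothing about how many remain. A patient with one treatment left meets every listed criterion.

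At stake would be precision: enrolment could stop with fewer than 100 pairs. A patient might also receive blinded study drug without being able to contribute to the primary comparison.

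**Working it through.** **The plan's own figure.** 100 subjects × 2 treatments = 200 treatments. This matches exactly, so the target assumes that every subject completes both treatments. No power statement can be reproduced, because none is given.

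**Assumptions (not in the documents).** A share q of subjects gives only one treatment, with q = 5, 10, 15 or 20%. Power is for a two-sided 5% paired t test (noncentral t). The effect is set so that 100 pairs give 80% power, which is a standardised paired difference of 0.283. This anchor is illustrative only.

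**Literal reading: single treatments count, and enrolment stops at 200 treatments.**
- Subjects: N = 200 / (2 − q)
- Pairs: N(1 − q)
- Example, q = 10%: N = 200 / 1.9 = 105.3; pairs = 105.3 × 0.9 = 94.7

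| q | Subjects | Pairs | Power | Shortfall from 80%, points |
|---|---|---|---|---|
| 5% | 102.6 | 97.4 | 79.0% | 1.0 |
| 10% | 105.3 | 94.7 | 77.8% | 2.2 |
| 15% | 108.1 | 91.9 | 76.5% | 3.5 |
| 20% | 111.1 | 88.9 | 75.1% | 4.9 |

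Without the power anchor, the standard error grows by √(100 / pairs): from √(100 / 97.4) = 1.013 to √(100 / 88.9) = 1.061. Intervals would be about 1 to 6% wider.

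**If enrolment stopped at 100 consents instead.** Pairs = 100(1 − q) = 95, 90, 85, 80, and power is 77.9, 75.6, 73.2, 70.5%. The plan calls 100 an estimate, so this is a harsher reading than the text requires.

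**What an entry criterion could add.** Suppose that requiring two planned treatments halved the loss and consents stopped at 100. Pairs would be 97.5, 95, 92.5, 90, and power 79.0, 77.9, 76.8, 75.6%. Against the plan that runs to 200 treatments, the gain is 0.0, 0.1, 0.3, 0.5 points. The gain is that small because 200 / (2 − q) = 100 / (1 − q/2): the present plan already takes 103 to 111 subjects, against 100 here. With 100 consents in both cases, the gain runs from 79.0 − 77.9 = 1.1 to 75.6 − 70.5 = 5.1 points. Halving is generous, because the criterion screens out only patients already known to have one treatment left. Cancelled treatments, withdrawals and missing readings remain.

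**What 100 complete pairs would cost, rounded up to whole subjects.**
- Criterion without effect, 100 / (1 − q): 106, 112, 118, 125 consents.
- Loss halved, 100 / (1 − q/2): 103, 106, 109, 112 consents.

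Without an effective criterion, the extra consents over the present plan are 100 / (1 − q) − 200 / (2 − q), which runs from about 3 at q = 5% to about 14 at q = 20%.

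**Paired reading.** If evaluable means usable in the planned paired test, 200 evaluable treatments are 200 / 2 = 100 pairs, and every shortfall above is zero.

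**The case for a change.** The strongest case for a change is that it costs two lines and settles when enrolment stops and who may be randomised. A stopping target should not have two defensible meanings. Eligibility is checked against the listed criteria, and neither list looks forward. The outcome definition makes counting single treatments a natural reading, and although the word initially in the Analytical Plan leaves room for further analyses, none is named that would use unpaired data.

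Much of this stands as description. Evaluable is undefined, the forward-looking criterion is unlisted, and the stated test drops subjects with one treatment. It does not stand that single treatments are bound to count towards the target. That is an inference, and the exact factor of two, in a paragraph that opens with the AB/BA design, points the other way. Nor is the eligibility gap open in practice. A patient known to have one treatment left cannot follow either randomised sequence, so staff would be unlikely to enrol one knowingly. Subjects who lose a planned second treatment would be lost under the new criterion too.

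**Conclusion.** The observation is accurate, but it identifies missing detail that the design itself supplies. Followed as written, the plan gives a valid within-subject comparison and breaks no power promise, because it makes none. Nothing in the documents shows that 100 pairs are needed or that 89 to 97 would be too few.

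On the less favourable reading of evaluable, with 5 to 20% of subjects giving one treatment and 80% power at 100 pairs (both assumed), the cost is 1.0 to 4.9 points of power. Recovering it takes about 3 to 14 more consents unless an entry criterion works, so most of the gain would come from a larger trial rather than from a repaired flaw. On the paired reading the cost is nil.

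The team could optionally state the target as 100 complete pairs, each with a baseline and a first post-stimulus systolic pressure at both study treatments, and could list the two-treatment expectation that the crossover already implies. That would tidy the wording. The analysis does not depend on it.

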### **Inclusion Criteria**

Age > /=18 years

Males or females

Anticipating electroconvulsive therapy to treat refractory mood disorders

### **Exclusion Criteria**

Under the age of 18

Allergy to alfentanil

Allergy to other standard anesthetic medications utilized in the course of ECT (glycopyrrolate, methohexitol, and succinylcholine)

History of malignant hyperthermia

History of severe airway obstruction, bronchospasm or laryngospasm

History of recent myocardial infarction, ventricular arrhythmia (within six weeks)

Adverse reaction to ECT requiring premedication with lidocaine or atropine

Non-English speaking

Patients unable to consent for themselves

Current pregnancy

Patients who have not yet received four treatments

Anesthesiologist uncomfortable with administering the study drug to the patient

## **Interventions and Interactions**

Informed consent will be obtained during the assessment with the psychiatrist involved in their care. The patient will be randomized into 2 groups: use of alfentanil with the first treatment or placebo with the first treatment and subsequently cross over to the other therapy for the second treatment. Study medication will be prepared by a member of the study team and the patient as well as all members performing anesthesia and data collection will be blinded to group allocation. All medications utilized in the conduct of this study are the standard anesthetic medications used on a daily basis (with the exception of the alfentanil) during the course of any patient having the ECT procedure and not enrolled in a research study.

A standardized anesthetic regimen will be utilized for each subject and includes the following:

### **HOLDING ROOM**

Glycopyrrolate 0.1 mg IV in the holding room.

Establish monitoring with baseline heart rate, blood pressures, manually recording each every 1 minute.

### **PRIOR TO INDUCTION**

Recording 3 minutes of blood pressures, pulse oximetry and electrocardiogram, every 1 minute monitoring

### **INDUCTION**

Standard induction for ECT with methohexitol 1 mg/kg and succinylcholine 1 mg/kg

After establishment of an adequate mask airway, and confirmation of adequate impedance on the ECT machine, the study medication (alfentanil or placebo) IV will be administered. A timer on the anesthesia monitor will be started.

### **60 SECONDS AFTER STUDY DRUG ADMINISTRATION**

ECT stimulus applied

During the procedure in the operating room, blood pressure and heart rate will be monitored as per standard of care (blood pressure every 1 minute and continuous electrocardiogram, pulse oximetry, and capnography while in the procedure room) until the patient is spontaneously ventilating adequately per anesthesia discretion. Hypertension will be treated if the systolic blood pressure exceeds 185 mmHg using nitroglycerin 400 mcg/mL per usual institutional practice. The full range of usual antiarrhythmic, vasopressor and antihypertensive medications including lidocaine, esmolol, phenylephrine, epinephrine, atropine and ephedrine will be available for use by the anesthesia team should they be required. Use of these medications will be tracked and recorded by the study team. After restoration of adequate spontaneous ventilation the patient will then be moved to recovery for subsequent discharge. Evaluation will be done by study personnel to assess the presence of headache or other potential adverse events prior to discharge, and patient satisfaction with the anesthetic.

Prior to discharge the subjects will be asked to rate the severity of headache (if present) as well as the satisfaction with the anesthetic received. Both will be rated on a scale of 0=no headache as all up to 10=worst headache ever, as well as 0=not satisfied with anesthetic at all up to 10=most definitely satisfied with the anesthetic received.

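### Does the missing time window for maximum and minimum heart rate bias the minimum-heart-rate comparison?

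*Combined protocol and SAP*

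**What the plan says.** Under Outcome Measure(s), the secondary outcomes include "maximum and minimum heart rates" with no window or data source. The same sentence gives other heart-rate outcomes fixed times: "within-individual differences of heart rate at 15 and 30 seconds post stimulus".

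Heart rate or ECG is recorded in three places: the holding room ("Establish monitoring with baseline heart rate"), the 3 minutes before induction, and the procedure room. The section on the 60 seconds after study drug describes standard-of-care monitoring in the room, with continuous ECG, "until the patient is spontaneously ventilating adequately per anesthesia discretion". The patient then moves to recovery. One secondary outcome is "time to return of spontaneous ventilation after induction"; total in-room time is another.

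The Induction section gives a usable time zero at study-drug administration: "A timer on the anesthesia monitor will be started". The Analytical Plan specifies a "paired T Test for continuous variables", with no term for length of observation. The Background describes the expected course as "an initial parasympathetic response rapidly followed by sympathetically mediated tachycardia and hypertension".

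**The concern.** Extremes depend on how long one looks. If the record ends when ventilation returns, its length is set after randomization, at a clinician's discretion, by an event the drug might influence. If alfentanil and placebo treatments were watched for different times, the treatment with the longer record would tend to show the lower minimum even with identical heart-rate behaviour. Pairing within subject would not help, because the imbalance would follow the treatment and not the person.

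A difference in minimum heart rate could then be read as bradycardia, or as protection from it, when it partly reflects observation time. The maximum is less exposed, because the peak is expected early and would fall inside both records. The primary outcome (first systolic pressure after the stimulus) and the heart rates at 15 and 30 seconds are tied to the stimulus and cannot be affected.

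**Working it through.** **Inputs from the documents.** About 100 subjects × 2 treatments = 200 treatments, which agrees with the stated target and gives 100 pairs. Study drug is given 60 s before the stimulus. The analysis is a paired t test. The documents give no alpha, SD, expected time to ventilation or heart-rate curve, so there is no planned figure to reproduce. Everything below on size rests on assumptions.

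**Step 1: conditions for bias.**

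| Condition | What the documents say |
|---|---|
| The in-room monitoring period is the outcome window | Not stated; the sentence describes standard-of-care monitoring |
| Observation time differs by treatment | Not stated; ventilation time and in-room time are only listed for comparison |
| The lowest rate falls late | Not stated; the Background's early parasympathetic phase points the other way |

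**Step 2: size of the shift if all three held.** Assume identical heart-rate behaviour at both treatments and records ending 300 s versus 360 s after the stimulus. The model uses 15 s epochs with a dip of 0, 10, 20 or 40 bpm in the first 15 s, then a peak of +35 bpm at 45 s. Decay is exponential with time constant 60 or 120 s. Residual SD is 5, 8 or 10 bpm and autocorrelation 0.5 or 0.9. Mean shift in the minimum, longer minus shorter record:

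| Early dip | Record from study drug | Record from stimulus |
|---|---|---|
| none | -0.6 to -1.4 bpm | -0.9 to -2.4 bpm |
| 20 bpm | 0 to -0.6 bpm | 0 to -0.6 bpm |
| 40 bpm | about 0 | about 0 |

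With a 10 bpm dip and a record from study drug, the shift is -0.1 to -1.0 bpm. The mean maximum stays within about 0.15 bpm of zero throughout.

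**Step 3: effect on the test.** For mean shift δ and SD of paired differences s, the t statistic is centred near δ × √100 / s = 10δ/s. If each treatment day has its own heart-rate level with SD σ, independent between days, s² includes 2σ². With σ = 5 that adds 2 × 25 = 50; with σ = 8 it adds 2 × 64 = 128. Leaving σ out makes s too small and the false-positive rate too high. For the record from study drug with no dip (two-sided 5%, 100 pairs):

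- σ = 0: 17–44%.
- σ = 5 to 8 (assumed): about 8–22%.
- Record starting before induction, σ = 5: shift about -0.1 to -0.8 bpm, rate about 4–9%.

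With a 20 or 40 bpm early dip the rate is 3–7% even at σ = 0, which is nominal within simulation error.

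**Step 4: a second model.** This one uses 5 s sampling, autocorrelated noise SD 4 bpm and day-level SD 5 bpm, again 300 versus 360 s:

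| Assumed course | Shift in minimum | False-positive rate |
|---|---|---|
| Flat after the peak | -0.6 bpm | 10% |
| Still falling late | -1.6 bpm | 44% |
| Deep early bradycardia | about 0 | about 5% |

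The still-falling curve has an imposed late slope of 0.02 bpm per second. Over the extra 60 s that is 0.02 × 60 = 1.2 bpm, most of its 1.6 bpm shift. With equal 300 s records the three curves give shifts of -0.08 to -0.01 bpm and rates of 4.9–5.8%.

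**The case for a change.** The strongest case for acting is that the omission is plain on the page, the mechanism is sound, and a definition would cost a few sentences. Heart rates at 15 and 30 seconds have times and the extremes do not. By listing ventilation time and in-room time as outcomes, the plan allows that treatment might change them. If pre-induction readings count, an extreme could predate the study drug and dilute the comparison. Large false-positive rates remain possible under some curves: 44% when the rate is still falling late, even with day-to-day variation included. A record starting at the stimulus with no early dip gives larger shifts than one starting at study drug.

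Much of this stands. The window is undefined, and a careful analyst should state the one used. What does not follow is that the plan as written leads to a wrong result:

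- The high rates need a late low and a treatment difference in record length, and the documents support neither.
- The highest heart rate during the anesthetic, and the lowest, are legitimate randomized outcomes in their own right. A longer stay with a lower recorded minimum is then partly a consequence of treatment. A fixed window answers a different question and would leave a late low value out of the comparison.
- A fixed window needs an end time, and the documents give no durations from which to choose one. They say the ECG runs continuously but not that traces are stored for analysis, and holding-room values are recorded manually each minute. A remedy without extra recording is therefore not assured.
- Ventilation time and in-room time will be compared by treatment anyway. They are imperfect proxies for time observed after the stimulus, but they would reveal a material imbalance.

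**Conclusion.** No change to the plan is needed. The gap is real but is one of detail, in two of many secondary outcomes. Analysts can fill it by stating which recording period supplied the extremes and applying the same rule at both treatments. Whether to use a fixed window or the whole procedure is a choice on which reasonable statisticians differ.

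The bias is conditional on all three requirements being met. Its illustrative size is a little over 1 bpm at most for one extra minute of record from study drug, and up to 2.4 bpm if the record starts at the stimulus with no dip at all. It is close to zero if the low comes early and deep. Record lengths, curve shapes, dip depths and the between-day SD are all assumptions. Evidence that alfentanil materially changes observation time, together with lows occurring late in the record, would call for caution in reading the minimum-heart-rate result. It would not affect the primary outcome or the heart rates at fixed times.
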